9.2 Special Studies

9.2.1 Neuroimaging Studies

Standard MRI will be obtained within 2 weeks prior to registration, at the end of radiation therapy (week 10), within 1 week prior to courses 3, 5, and 8 of maintenance and at the end of treatment. MR perfusion and permeability studies and DTI will also be obtained at the same time points as standard MRI through week 26 (6 months from initiation of treatment).

For patients showing possible tumor progression on MRI during the first 6 months after the initiation of ABT-888 and irradiation (on scheduled MRI studies), the treating physician will have the option of allowing the patient to remain on study, continuing protocol therapy, and repeating disease reassessment in 4-6 weeks. The investigational sequences should be obtained on this additional scan which is completed due to possible pseudoprogression. 3T imaging is the preferred modality of choice.

Standard MR imaging will include Sagittal T1 MPRAGE, axial FLAIR, axial T2,

postgadolinium sagittal T1 MPRAGE (with reconstructions) and axial T2 images. Protocol standard parameters will be distributed to the sites and posted on the PBTC NIC website.

Volumetric analyses will be done at the Neuroimaging Center (NIC, Children's Hospital Boston) via the Vitrea (VitreaTM) workstation, from the axial FLAIR and T1-weighted post-contrast brain images.

9.2.2 MRI Permeability and Perfusion Imaging

The perfusion protocol will be performed using T1-weighted dynamic contrast-enhanced (DCE) permeability MRI to assess immediate biological activity followed by T2*-weighted dynamic susceptibility contrast (DSC) perfusion MRI technique. DSC perfusion MRI dynamics will allow assessment of the hemodynamic parameter relative cerebral blood volume (rCBV). DCE permeability MRI metrics will include the volume transfer constant between plasma and extravascular extracellular space (K^{trans}), fractional blood-plasma volume (V_p), and the volume of the extravascular extracellular space per unit volume tissue (V_e). Both DCE and DSC MRI-derived data will be complementary to conventional contrast-enhanced MR imaging.

9.2.2.1 DCE permeability MRI

Please note that there will be a total of 5 sequences: 4 for T1 mapping and the DCE with injection). Also, it is important that the same patient MUST be scanned on the same exact scanner (not just the brand/tesla, but actual scanner) if more than one exam is to be done. A 3D (not 2D) fast gradient echo type of sequences (fast SPGR, FLASH, THRIVE) must be used. This will be performed as 3D slab in the axial plane. Normalization or intensity correction or flow correction filters such as CLEAR, SCIC or PURE must not be used for any of the series. The slice locations and positioning for the T_1 mapping and the dynamic series *MUST* be identical (same matrix, slices, FOV, TR, TE, except NEX and FA). Hence copying of the slices is needed. The TR and TE for all 4 series (4 T_1 maps plus a dynamic series) should be identical. For GE systems, reduce Turbo Factor to 1 or 0 if TR and TE do not match across series. T₁ Maps should be acquired with 2 signal averages and the Dynamic Series with 1. Temporal Resolution of "T1 DCE" series (scan time per phase/measurement) should be less than or equal to 6 Seconds, with NO gaps between phases. ASSET/IPAT/Parallel Imaging Parallel imaging is set to be OFF, however, if it is not possible to achieve a temporal resolution of less than 6 seconds, this should be set to a factor of 2. The dynamic series should last 5 minutes in total scan time (excluding T1 mapping series).

The table below describes the image acquisition parameters for the T_1 map sequences as well as the dynamic scan, *in the order of acquisition (first T1 maps then T1 DCE)*. Make sure this happens *before* DSC perfusion MRI.

The first half dose of contrast agent to be administered 20 sec into "T1 DCE" sequence. Do NOT inject prior to T1 DCE or during T1 maps (see **Table 16** and **Table 17** below).

	Table 16							
	"T1 DCE"							
Series Name Sequence Flip Angle Notes								
T1 map15	3D fast GRE	15 degrees	Axial, 2 NEX					
T1 map10	3D fast GRE	10 degrees	Axial, 2 NEX					
T1 map05	3D fast GRE	5 degrees	Axial, 2 NEX					
T1 map02	3D fast GRE	2 degrees	Axial, 2 NEX					
T1 DCE	Dynamic Series, 3D fast GRE	15 degrees	Axial, 1 NEX, inject 20 sec into this					

3D T1W specs for T₁ Maps and Dynamic Series						
Sequence type	Spoiled gradient echo					
Imaging mode	3D					
Slice orientation	Axial					
Frequency direction	A/P					
Phase direction	R/L					
FOV - frequency	220 mm					
FOV - phase	220 mm					
Matrix - frequency	256					
Matrix - phase	160-192					
In-plane resolution	$\leq 1 \text{ mm}$					
Fat-suppression	No Fat Sat					
TR	~4 msec					
ТЕ	Less than 2 ms or min full					
TI (STIR sequence)	N/A					
Flip Angle	DCE -15 degrees; T1 maps - 2, 5, 10 and 15					
Slice thickness (acquired, not interpolated)	5mm, maximum 6mm					
Number of slices	Minimum 10 prior to zero fill					
Slice Gap	No gap					
Parallel imaging factor	≤ 2					
Number of averages	1 for DCE, 2 for T1 maps					
k-space ordering	standard, non-centric					
Temporal Resolution of "T1 DCE": (seconds per	\leq 6 seconds					
phase/measurement)						
"T1 DCE" imaging duration	\geq 5 minutes					

Table 17

Run the Dynamic multi-phase "T1 DCE" at flip angle of 15 degrees – enable multi-phase (on GE systems) and increase the number of phases (or measurements) until the scan time is **six** minutes. Contrast injection should be delivered at 20 sec into T1 DCE, not earlier. Injection rate is 2 ml/second at 0.05 mmol/kg body weight followed by a 10 cc saline flush at the same rate (all should use the same type of contrast agent).

9.2.2.2 *Diffusion tensor imaging*

Diffusion tensor imaging (DTI) or axial T2 weighted imaging can be performed between the DCE and DSC MRI acquisitions. In addition to providing permeability metrics, the gadolinium contrast agent from the DCE acquisition will also serve as a "preload" to help correct for leakage effects for the DSC perfusion acquisition.²⁰

9.2.2.3 DSC perfusion MRI

An axial 2D T2* GRE-EPI sequence will be used. TR = 2000 ms, TE = 23 ms, matrix = 128 x 128, FOV = 240 mm, frequency direction R-L, slice thickness = 5.0 mm with 2 mm gap, flip angle = 60 degrees, NEX = 1. Repeat 50-60 times. Total acquisition time ~ 2 minutes. Begin bolus injection (2 ml/sec) of 0.05mmol/kg BW GdDTPA at 20secs after scanning starts followed by a 10 cc saline flush at the same rate. Regional rates of transverse relaxation enhancement (Δ R2*) during contrast agent passage will be calculated from: Δ R2*(t) = (-1/TE) In [S(t)/S(0)] from which estimates of rCBV will be derived.

Perfusion MR images will be transferred to the GE Advantage Workstation (4.3.05); Functool (4.4.05) (GE Healthcare, Milwaukee, WI) to calculate rCBV maps on a voxel-wise basis. User defined regions of interest (ROIs) measuring 3-5 mm will be placed within areas that demonstrate maximal CBV based on color-overlay maps. Effort will be made to exclude large vessels and necrotic-appearing regions from the ROIs. An ROI will also be placed in the frontal normal appearing white matter (NAWM) to provide relative CBV (rCBV) values to normalize perfusion data and enable comparison between patient and between serial studies.¹⁸

Permeability MR Images will be transferred to the iCAD Workstation (iCAD, Inc., Nashua, NH). This utilizes a 2 compartmental pharmacokinetic model allowing voxel-wise calculation of K^{trans} , V_p , and V_e . User defined ROIs encompassing the entire contrast-enhancing lesion as well as multiple smaller 3-5 mm ROIs will be placed within areas that demonstrate maximal K^{trans} , V_p , and V_e based on color-overlay maps. Effort will be made to exclude large vessels and necrotic-appearing regions from the ROIs.

9.2.3 MR Diffusion Imaging

MR Diffusion Imaging will consist of 35 direction DTI sequences: slice thickness 2.2 mm, TR= 8800 ms, TE= 88ms, FOV 220 mm, b value= 1000 s/mm², 35 directions. Full protocol will be provided on the PBTC NIC website.

9.2.4 Image Transfer

Standard MRI, perfusion/ permeability and DTI images will be electronically transferred to the PBTC Neuroimaging Center (NIC). All patient specific data are stripped from the images and replaced with PBTC case-ids prior to sending images to the NIC. All image data transfer is accomplished using PGP (pretty-good-privacy) 128-bit encryption which meets industry standard for secure communication.

9.2.5 Central Review

Central review of imaging studies will be conducted through the PBTC Neuroimaging Center (NIC). The director and one neuroradiologist at NIC will review the imaging studies for response and pseudo-progression at study completion. Post processing of perfusion/permeability studies will be done at USC.

10. STUDY CALENDAR

		r	Fable 1	8				
	Standard (linical and l	Laborator	y Assessmen	ts – Phase I			
	Pre- therapyABT888 and Radiation (Course 1.1)Maintenance (Courses 2.1 – 2.23)				End of Treatment			
PHYSICAL ASSESSMENTS		ABT 888 + RT	Rest Period	Week 10 - 11 ¹⁰	Weekly Courses 1-10	Prior to Courses 2-10	Extended Therapy Courses 11-23	
Medical history, physical exam and diary review	Х	Weekly	X9	Х		Х	X ¹²	Х
Vital signs	Х	Weekly	X ⁹	Х		Х	X ¹²	Х
Performance status	Х	Weekly	X ⁹	Х		Х	X ¹²	Х
Neurologic exam	Х		X ⁹	Х		Х	X ¹²	Х
Height, Weight, BSA	Х		X ⁹	Х		Х	X ¹²	
LABORATORY EVALUATIONS								
CBC (WBC, Hgb, Hct, Platelets, ANC, ALC)	Х	Weekly ¹	X ⁹	Х	\mathbf{X}^1		X ¹³	Х
Serum Chemistry (Electrolytes, BUN, Creatinine, Calcium, Magnesium, Phosphorous, SGOT(AST), SGPT(ALT), Total Bilirubin, Albumin)	Х	Weekly ²	X ⁹	х		X ²	X ¹³	Х
Pregnancy test ³	Х			Х		Х	Х	
IMAGING ASSESSMENTS								
Brain MRI	X^4			X^4		X ^{4,11}	X^{14}	X^{11}
MRI Perfusion/Permeability	X^4			X^4		X 4,11		X^{11}
Diffusion Tensor Imaging (DTI)	X^4			X^4		X 4,11		X ¹¹
Correlative Studies								
Pharmacokinetic Studies ⁵	Х	Х						
Biology Study (PARP,NHEJ and γ H2AX) in PBMC's ⁶	Х	Х			X^6			
Biology study – pre-trial tumor material	X^7							
Urine Biomarker ⁸	Х			Х		X ⁸		

 CBC is done weekly for all courses. Patients with dose limiting hematologic toxicity (≥Grade 3 thrombocytopenia or Grade 4 neutropenia) should have CBC at least twice weekly (3-4 days apart) until toxicities improve to grade 2 or less

2. Patients with grade 3 or 4 non-hematologic toxicity should have relevant laboratory tests repeated twice weekly (3-4 days apart) until they recover to grade 2 or less

3. Serum or urine pregnancy test is to be repeated within 72 hours prior to enrollment in females of childbearing potential and prior to each course during maintenance

- 4. Neuroimaging assessments are to be completed within 2 weeks of registration, at the end of radiation + ABT888, (week 10-11), within 1 week prior to courses 3, 5, 8 and at the end of maintenance. See footnote #11 for details of investigational imaging procedures. For patients with possible tumor progression on week 10, 18, or 26 imaging studies, see guidelines in section 2.4.2 or 11.1.4 for frequency of next imaging study.
- Participation in the pharmacokinetic study is required for the Phase I portion of the study. See section 9.1.1 for collection schedule

6. Participation in the correlative biology study in PBMC's is **optional**. See section 9.1.2 for collection schedule

- 7. Participation the biology study pre-trial tumor material is optional. See section 9.1.3 for processing and shipping instructions.
- 8. Participation in the urine correlative study is optional. Urine samples should be collected at the time of each scheduled MRI (section 9.1.4)
- 9. During the rest period, each patient should have at least one visit between weeks 7 and 10.
- 10. Laboratory tests and assessments may be completed ±1 week of week 10, prior to starting Maintenance.
- 11. For patients showing possible tumor progression on MRI during the first 6 months after initiation of ABT-888 and radiation (on required MRI studies performed at week 10, week 18, or 26), the treating physician will have the option of allowing the patient to remain on study, continuing protocol therapy, and repeating disease reassessment in 4-6 weeks. The repeat MRI should include MRI perfusion/permeability and DTI. *MRI Perfusion/Permeability and DTI will only be obtained on routine MRI studies through week 26; the investigational sequences should be obtained on a scan 4-6 weeks after the week 26 study IF the patient is being handled as a potential pseudoprogression.*

12. If a patient receives more than 10 courses, evaluations in subsequent courses should be obtained at the discretion of the treating physician

- 13. It is recommended that labs be obtained at least every two weeks during the extended treatment period (i.e. beyond course 10).
- 14. It is recommended that standard MRI scans should be done at least every three months during the extended treatment period (i.e. beyond course 10).
- Additional studies may be done as clinically indicated at the investigator's discretion.

Note: Obtain other studies as clinically indicated

Pre-therapy laboratory evaluations within 7 days of starting treatment will be considered Day 1, Course 1 evaluations

		-	able 1)				
	Standard C	linical and L	aboratory	y Assessment	ts – Phase I	I		
	Pre- therapyABT888 and Radiation (Course 1.1)Maintenance (Courses 2.1-2.23)				End of Treatment			
PHYSICAL ASSESSMENTS		ABT 888 + RT	Rest Period	Week 10 - 11 ¹⁰	Weekly Courses 1-10	Prior to Courses 2-10	Extended Therapy Courses 11-23	
Medical history, physical exam and diary review	Х	Weekly	X ⁹	Х		Х	X^{12}	Х
Vital signs	Х	Weekly	X ⁹	Х		Х	X ¹²	Х
Performance status	Х	Weekly	X9	Х		Х	X ¹²	Х
Neurologic exam	Х		X9	Х		Х	X ¹²	Х
Height, Weight, BSA	Х		X9	Х		Х	X ¹²	
LABORATORY EVALUATIONS								
CBC (WBC, Hgb, Hct, Platelets, ANC, ALC)	Х	Weekly ¹	X ⁹	Х	\mathbf{X}^{1}		X ¹³	Х
Serum Chemistry (Electrolytes, BUN, Creatinine, SGOT(AST), SGPT(ALT), Total Bilirubin,)	Х	Weekly ²	X ⁹	Х		X ²	X ¹³	Х
Pregnancy test ³	Х			Х		Х	Х	
IMAGING ASSESSMENTS								
Brain MRI	X^4			X^4		X ^{4,11}	X^{14}	X^{11}
MRI Perfusion/Permeability	X^4			X^4		X 4,11		\mathbf{X}^{11}
Diffusion Tensor Imaging (DTI)	X^4			X^4		X ^{4,11}		X^{11}
Correlative Studies								
Pharmacokinetic Studies ⁵	Х	Х						
Biology Study (PARP,NHEJ and γH2AX) in PBMC's ⁶	Х	Х			X^6			
Biology study – Pre-trial tumor material ⁷	X							
Urine Biomarker ⁸	Х			Х		X ⁸		

Table 19

1. CBC is done weekly for all courses. Patients with dose limiting hematologic toxicity (≥Grade 3 thrombocytopenia or Grade 4 neutropenia) should have CBC at least twice weekly (3-4 days apart) until toxicities improve to grade 2 or less

2. Patients with grade 3 or 4 non-hematologic toxicity should have relevant laboratory tests repeated twice weekly (3-4 days apart) until they recover to grade 2 or less

3. Serum or urine pregnancy test is to be repeated within 72 hours prior to enrollment in females of childbearing potential and prior to each course during maintenance

4. Neuroimaging assessments are to be completed within 2 weeks of registration, at the end of radiation + ABT888, (week 10-11), within 1 week prior to courses 3, 5, 8 and at the end of maintenance. See footnote #11 for details of investigational imaging procedures. For patients with possible tumor progression on week 10, 18, or 26 imaging studies, see guidelines in section 2.4.2 or 11.1.4 for frequency of next imaging study.

5. Participation in the pharmacokinetic study is optional for the Phase II portion of the study. See section 9.1.1 for collection schedule

6. Participation in the correlative biology study in PBMC's is **optional.** See section 9.1.2 9.1.2 for collection schedule

- 7. Participation in the correlative biology study pre-trial tumor material is optional. See Section 9.1.3 for processing and shipping instructions
- 8. Participation in the urine correlative study is optional. Urine samples should be collected at the time of each scheduled MR (section 9.1.4)
- 9. During the rest period, each patient should have at least one visit between weeks 7 and 10.
- 10. Laboratory tests and assessments may be completed ± 1 week of week 10, prior to starting Maintenance.
- 11. For patients showing possible tumor progression on MRI during the first 6 months after initiation of ABT-888 and radiation (on required MRI studies performed at week 10, week 18, or 26), the treating physician will have the option of allowing the patient to remain on study, continuing protocol therapy, and repeating disease reassessment in 4-6 weeks. The repeat MRI should include MRI perfusion/permeability and DTI. *MRI Perfusion/Permeability and DTI will only be obtained on routine MRI studies through week 26; the investigational sequences should be obtained on a scan 4-6 weeks after the week 26 study IF the patient is being handled as a potential pseudoprogression.*
- 12. If a patient receives more than 10 courses, evaluations in subsequent courses should be obtained at the discretion of the treating physician
- 13. It is recommended that labs be obtained at least every two weeks during the extended treatment period (i.e. beyond course 10).
- 14. It is recommended that standard MRI scans should be done at least every three months during the extended treatment period (i.e. beyond course 10). Additional studies may be done as clinically indicated at the investigator's discretion.

Note: Obtain other studies as clinically indicated

Pre-therapy laboratory evaluations within 7 days of starting treatment will be considered Day 1, Course 1 evaluations

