5.1.1.1 Dose-finding Period for the Phase I study

The observation period for DLTs (Course 1) during Phase I of the study includes the entire duration of radiation therapy (approximately 6 to 7 weeks, allowing for delays in XRT for holidays, mask adjustments, etc.) and the rest period between the end of radiation therapy and the start of maintenance treatment on week 11. Dose limiting toxicities are defined in section 5.2. Guidelines for dose modifications (if required) are provided in section 6.1.

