5.1.2 Drug Administration during Radiation - Phase II

The Phase II portion of the trial is to evaluate the efficacy of ABT-888 and radiation therapy (at the maximum tolerated or recommended ABT-888 dose level from the Phase I study), followed by maintenance therapy with 10 cycles of ABT-888 and temozolomide in patients with newly diagnosed DIPG. Follow instructions for administering ABT-888 during radiation for the Phase II portion of the study as previously outlined in section 5.1.1.

5.1.3 Drug Administration - Maintenance Therapy (Phase I and Phase II) Maintenance therapy of ABT-888 and TMZ will begin approximately at week 11 (3-4 weeks after the completion of irradiation and ABT-888) provided that the patient's bone marrow, renal, and hepatic organ functions continue to meet on study criteria. ABT-888 will be given twice daily, with the morning dose given 60-120 minutes prior to the daily dose of TMZ. ABT-888 and TMZ will be given on day 1-5, and each course of treatment will be a minimum of 28 days in length (Table 11).

Table 11						
Schema- Maintenance Phase of Therapy						
Each Course	May receive a maximum of 10 courses					
Day	1	2	3	4	5	6-28
ABT-888, BID	x,x	x,x	x,x	x,x	x,x	Rest/Evaluation
Temozolomide, once daily	Х	Х	Х	Х	Х	Rest/Evaluation

All patients (Phase I and Phase II), will start maintenance therapy on week 11 with 25 mg/m² bid

of ABT-888 and 135 mg/m²/day of TMZ (the starting dose for maintenance therapy, Table 12), for 5 days every 28 days, which represent the recommended phase II doses from PBTC-027. **Dosing of ABT-888 and TMZ will be based on the BSA determined prior to each course.** Since this dose determination was based on children with refractory brain tumors, many of whom were heavily pre-treated, it is possible that children with newly diagnosed DIPG, who are chemotherapy naïve at entry, will tolerate higher doses of ABT-888 and TMZ during maintenance.

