13. STATISTICAL CONSIDERATIONS

13.1 Phase I Study Design/Endpoints

13.1.1 Dose Finding

This phase of the trial is being implemented in order to determine maximum tolerated dose or recommended Phase II of ABT-888 that can safely be delivered with RT in the context of carrying it forward to the efficacy (Phase II) component of this study. The traditional 3+3 dose finding algorithm will be used. Initially 3 patients will be enrolled on dose level 1 and will be observed for dose limiting toxicities during the first 10 weeks (6-7 weeks of radiation therapy followed by a rest period), which is the DLT observation period. If none of these three patients experience a DLT, escalation to dose level 2 will occur. If, on the other hand, 1 out of three patients experience a DLT, then 3 additional patients will be treated at dose level 1. If at most 1 DLT is observed in these 6 patients, escalation to dose level 2 will occur. Otherwise, if 2 or more DLTs are observed in dose level 1, then de-escalation to dose level 0 will take place and the same process will be repeated. The highest dose level with fewer than 2 DLTs in 6 patients will be carried forward to the Phase II component of this study. If dose level 0 is determined to be too toxic (i.e. more than 1 DLT), then the trial will be closed to accrual and the approach will be re-evaluated.

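### The Phase I calendar contradicts itself on how often blood counts are taken in the rest period, which is 3-4 of the 10 weeks of the DLT window

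*Combined protocol and SAP*

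**What the plan says.** **The window.** Section 5.1.1.1 states: "The observation period for DLTs (Course 1) during Phase I of the study includes the entire duration of radiation therapy", and adds the rest period up to the start of maintenance in week 11. Section 5.2.1 gives the window as weeks 1 through 10. Section 13.1.1 says that patients "will be observed for dose limiting toxicities during the first 10 weeks (6-7 weeks of radiation therapy followed by a rest period". Section 5.1.3 starts maintenance "3-4 weeks after the completion of irradiation and ABT-888".

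**The event.** Section 5.2.1.3 counts any thrombocytopenia of grade 3 or higher, or grade 4 neutropenia, as a hematologic DLT. It sets no minimum duration.

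**The counts.** Table 18 has three relevant CBC cells:
- During ABT-888 plus radiation: weekly, with footnote 1.
- Rest Period: an X with footnote 9 only, "During the rest period, each patient should have at least one visit between weeks 7 and 10".
- Week 10-11: an X. The column heading carries footnote 10: "Laboratory tests and assessments may be completed ±1 week of week 10, prior to starting Maintenance".

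Footnote 1 opens with a general rule: "CBC is done weekly for all courses". Both footnote 1 and section 6.1.2 call for twice-weekly counts, but only once a hematologic DLT is known.

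**The concern.** The two rules lead to different data. If footnote 1 governs, ascertainment of hematologic DLTs is even across the window. If the Rest Period cell governs, counts are weekly for 6-7 weeks and then fall to two, or in effect one, over the remaining 3-4 weeks. A low count that comes and goes between draws would not be recorded as a DLT.

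Under section 13.1.1 the DLT count alone drives escalation and de-escalation, and the highest level with fewer than 2 DLTs in 6 patients goes to Phase II. A missed DLT can only make a dose look safer than it is. It also means that the closer follow-up triggered by a known DLT does not start. Section 6.1.2 ties platelet support to the risk of intra-tumoral hemorrhage.

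The conflict also touches evaluability. Section 13.1.2 lets the study chair declare inevaluable, and replace, a patient who completes therapy without meeting all specified monitoring requirements. With two schedules, it is unclear what complete monitoring means in the rest period.

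**Working it through.** **1. Length of the rest period.** Section 5.1.4.5 prescribes 30 fractions. At 5 per week, 30/5 = 6 weeks, and 10 - 6 = 4 weeks of rest. With 7 weeks of radiation the rest is 10 - 7 = 3 weeks. This reproduces the 10-week window and the 3-4 week gap; the rest is 30-40% of the window.

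**2. Counts between radiation and maintenance under each rule.**
- Footnote 1: weekly, so 3-4.
- Table cells: one rest visit plus Week 10-11, so 2.
- Table cells with the rest visit at week 10, alongside the Week 10-11 evaluation: in effect 1.

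**3. Chance that an episode is seen.** The documents give neither episode length nor timing. Assume an asymptomatic episode of L days with onset uniform over a rest of R days, seen only if a count falls within it. For k counts equally spaced with the last on day R, detection = min(1, kL/R).

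| Rest and counts | L=5 | L=7 | L=10 | L=14 |
|---|---|---|---|---|
| 28 days, weekly (k=4) | 71% | 100% | 100% | 100% |
| 28 days, two (days 14, 28) | 36% | 50% | 71% | 100% |
| 28 days, one (day 28) | 18% | 25% | 36% | 50% |
| 21 days, two (days 10.5, 21) | 48% | 67% | 95% | 100% |

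For example, two counts and L = 7 give 2 × 7/28 = 50%.

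**4. Effect on the 3+3 decision.** The plan states no operating characteristics for the rule, so there is no figure to reproduce. From section 13.1.1, a dose is cleared with 0 DLTs in 3, or 1 in 3 followed by 0 in the next 3:

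C(p) = (1-p)³ + 3p(1-p)²(1-p)³.

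Assume a true DLT rate of 33%. With full detection, C(0.33) = 0.301 + 0.134 = 0.434.

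Let f be the share of DLTs that are laboratory-only events starting in the rest period, and s the detection probability from step 3. The observed rate is p' = 0.33 × [1 - f(1-s)]. For 7-day episodes:

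| Counts | f=10% | f=25% | f=40% |
|---|---|---|---|
| Weekly (s=1) | 43% | 43% | 43% |
| Two, 28-day rest (s=0.50) | p'=0.314, C=47% | p'=0.289, C=52% | p'=0.264, C=57% |
| One at day 28 (s=0.25) | p'=0.305, C=48% | p'=0.268, C=56% | p'=0.231, C=64% |
| Two, 21-day rest (s=0.67) | p'=0.319, C=46% | p'=0.303, C=49% | p'=0.286, C=52% |

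For 14-day episodes, two counts detect everything in this model and C stays at 43%.

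**The case against.** The strongest reply is that the weekly rule is already in the protocol. Footnote 1 covers all courses, section 5.1.1.1 makes the rest period part of Course 1, and Table 18 heads the radiation block as Course 1.1. Footnote 9 sets a floor on visits and is shared with history, vital signs, performance status and the neurologic examination. A floor on visits is compatible with weekly counts, since section 3.4 allows laboratory studies at any CLIA-certified laboratory. This stands in part: a careful site could read the calendar this way. But the Rest Period CBC cell drops both the word weekly and the footnote 1 marker that the radiation cell carries, so a site following the cell would also have a fair claim to compliance.

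The second reply is that the effect may be small. ABT-888 is not given in the rest weeks, a cytopenia that begins during radiation and persists would probably be caught by the weekly counts, and longer episodes are seen under either schedule. Section 2.2.2.2 reports no DLT in 13 adults (6 at 50 mg and 7 at 100 mg bid) given ABT-888 with whole-brain irradiation. Section 2.3.4 links dose-limiting hematologic toxicity to the combination with TMZ. This also stands: it argues for caution about size, not about direction.

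A reader might infer that only one blood count is required in the whole rest period. The documents do not support that, because Week 10-11 is a separate scheduled count. Nor does the matching footnote in Table 19 bear on dose selection, since that is the Phase II calendar.

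**Conclusion.** The point holds as an internal contradiction that affects ascertainment of the Phase I primary endpoint. Table 18 does not settle whether counts in 30-40% of the DLT window are weekly, or two, or in effect one. Where a site follows the cell, short hematologic DLTs can be missed, and any miss pushes the 3+3 decision toward a higher dose.

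The size cannot be derived from the documents. The illustration (43% rising to 47-57% with two counts over 28 days, or to 48-64% with one) rests on an assumed true DLT rate of 33%, 7-day asymptomatic episodes, uniform onset, and 10-40% of DLTs being laboratory events that start in the rest period. With a 21-day rest and two counts it is 46-52%; with 14-day episodes and two counts there is no effect.

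It would be tempting to conclude that the observed DLT rate is biased low, or that the Phase II dose will be too high. The documents do not support either as a statement of fact: the bias arises only where the cell is followed in preference to footnote 1, and only if short events occur in the rest weeks.

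**What to change.** For Phase I, reconcile the Rest Period CBC cell in Table 18 with footnote 1, so that one count frequency, consistent with the weekly rule already stated, applies through the end of the DLT window, that is, to the start of maintenance. Keep footnote 9 for the clinic-visit items.

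The sponsor may also state whether serum chemistry is drawn with those counts. That is optional: footnote 1 concerns the CBC only, and nothing in the calendar calls for weekly chemistry in the rest period.

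The cost is a calendar amendment and about 1-3 extra CBC draws per Phase I patient: 3-4 weekly counts less the 2, or in effect 1, that the cells now require. Section 13.3 expects 12-18 Phase I patients, so the total is roughly 12 to 54 draws. Section 3.4 allows them at a local CLIA-certified laboratory, so no extra visit to the primary institution is needed.
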